1.2. Schema

Figure 1. Overall Study Schema for Cohorts 1 and 2

[figure not shown]
[figure not shown]
[figure not shown]

Figure 2. Overall Study Schema for Cohort 3

[figure not shown]
[&]quot;T" denotes visit planned as a telephone contact

Figure 3. Titration Schema for Cohorts 1 and 2

^{*} Placebo (Arm 1) n=67 which includes Cohort 1 (n=60) and Cohort 2 (n=7). The 2-week titration arms (Arms 7, 8 and 9) n=34 per arm which includes Cohort 1 (n=20) and Cohort 2 (n=14).

Figure 4. Titration Schema for Cohort 3

1.3. Schedule of Activities (SoA)

PROCEDURES section of the protocol for detailed information on each procedure and assessment required for compliance with the protocol. The investigator may schedule visits (unplanned visits) in addition to those listed in the SoA table, in order to conduct The SoA table provides an overview of the protocol visits and procedures. Refer to the STUDY ASSESSMENTS AND evaluations or assessments required to protect the well-being of the participant.

1.3.1. SoA for Cohorts 1 and 2

| Protocol Activity (See Appendix 11 for abbreviations) | Scree Ph | Screening Phase | | | | • • | Freatment Phase | ent Ph | ase | | | | End of Treat- ment ^a | Follow-up ^b | | Early Term/ Dis- |
|--|-------------|--------------------|------------------|----------|----------|----------|-----------------|----------|----------|----------|----------|---------------|---------------------------------------|------------------------|-----------|--------------------------------|
| ¥2 | Screen | Pbo run-in | | | | | | | | | | | | | o n | contin- uation ^c |
| Study Parth | | | | | | Part A | t A | | | | | Part B | | | | |
| Weeks Relative to Dosing on Day 1 | | | 0 | 2 | 4 | 9 | 8 | 10 | 12 | 16^{a} | 18 | 22 | 26 | 27-28 | 30-31 | ET |
| Days Relative to Dosing on Day 1 ^d | -42 | -14±3 | 1 | 14±3 | 28±3 | 42±3 | 26±3 | 70±3 | 84±3 | 112±3 | 126±3 | 154±3 | 182±3 | 189- | 210- | |
| | cl- 01 | | 71. | 1 | ; | } | ; | , | , | 0.52.5 | 777. | - | 977. | - | 717 | |
| Visit | V1 | V2 | V3 | V4 | VS | 9A | V7 | 8. | 60 | V10 | V11 | V12 | V13 | V14 | $V15^{e}$ | |
| Informed consent & demography | X | | | | | | | | | | | | | | | |
| Review of eligibility criteria | X | X | x | | | | | | | | | | | | | |
| Medical history | X | | | | | | | | | | | | | | | |
| SF-36v2® (all sites) ^f | | X | X | | | | | | | X | | | X | | | |
| PGI-S (US only) ^f | | X | X | X | X | X | Х | X | X | X | X | Х | X | | | |
| PROMIS®, IWQOL-Lite-CT® (US only) ^f | | X | X | | | | | | | X | | | Х | | | |
| PGI-C (US only) ^f | | | | | X | | | | | Х | | | Х | | | |
| Open-ended inquiry for AEs | X | | \uparrow | ↑ | ↑ | ↑ | ↑ | ↑ | ↑ | ↑ | ↑ | \rightarrow | ↑ | ↑ | X | х |
| Review prior/concomitant treatments | х | X | X | X | X | Х | X | X | Х | X | X | Х | Х | X | X | X |
| Review drug, alcohol, tobacco use | Х | X | х | X | X | х | X | X | X | Х | X | Х | Х | X | X | X |
| Review contraception use (females only) | Х | X | Х | X | X | х | X | X | X | Х | X | Х | X | X | X | X |
| Mental health questionnaires (C-SSRS, PHQ-9) | Х | X | X | X | X | X | X | X | X | Х | X | Х | Х | X | | X |
| Physical examination ^g | Х | | X | | | | | | | X | | | Х | X | | X |
| Body weight (in duplicate) ^h | Х | X | X | X | X | X | X | X | X | Х | X | Х | Х | X | | X |
| Waist and hip circumference (in triplicate) | Х | | х | X | X | х | X | X | X | Х | X | Х | Х | X | | X |
| Supine 12-lead ECG (pre-dose) | Х | X | X | X | X | х | X | X | X | Х | X | Х | Х | X | | X |
| Supine vital signs (in triplicate) (pre-dose unless noted) | × | x | \mathbf{x}^{i} | × | × | × | × | × | × | x | × | × | \mathbf{x}^{i} | × | | × |

| | Č | | | | | | | ř | | | | | | : | _ | |
|--|---------------|--------------------|----------|----------|----------|----------|----------------|----------|----------|----------------|----------------|------------------|---------------------------|-------------|----------------|--------------------------------|
| (See Appendix 11 for abbreviations) | Scre Ph | screening Phase | | | | | rearment Fnase | ent Pn | ase | | | | End of Treat- | ronow-up | | Eariy Term/ |
| | | | | | | | | | | | | | menta | | | Dis- |
| | Screen | Pbo run-in | | | | | | | | | | | | | ŏ = | contin- uation ^c |
| Study Parth | | | | | | Part | t A | | | | | Part B | | | | |
| Weeks Relative to Dosing on Day 1 | | | 0 | 2 | 4 | 9 | 8 | 10 | 12 | 16^a | 18 | 22 | 26 | 27-28 | 30-31 | ET |
| | -42 to -15 | -14±3 | 1 | 14±3 | 28±3 | 42±3 | £+95 | 70±3 | 84±3 | 112±3 | 126±3 | 154±3 | 182±3 | 189- 196 | 210- | |
| Visit | V1 | V2 | V3 | V4 | VS | 9.0 | V7 | 8.0 | 6/ | V10 | V11 | V12 | V13 | V14 | V15e | |
| Registration in trial (via IRT) | X | | | | | | | | | | | | | | | |
| Eating-Related Factors Daily Diary (US only) | | X | ↑ | ↑ | ↑ | ↑ | ↑ | ↑ | ↑ | ↑ | ↑ | ↑ | Х | | | |
| Dietary & physical activity counseling | | X | X | | X | | Х | | X | Х | х | Х | Х | | | |
| Review dosing diary | | X | X | X | X | X | Х | X | X | X | х | X | X | | | X |
| Randomization in trial (via IRT) | | | X | | | | | | | | | | | | | |
| Dispensation of study intervention supply & | | \mathbf{x}^k | X | X | X | х | х | X | X | \mathbf{x}^1 | \mathbf{x}^1 | \mathbf{x}^{1} | | | | |
| dosing diary | | | | | | | | | | | | | | | | |
| Dose study intervention on site (with food) | | х | Х | Х | X | х | х | X | X | Х | Х | Х | Х | | | |
| Compliance check of returned study | | | X | X | X | X | Х | X | X | Х | х | X | х | | | X |
| intervention | | | | | | | | | | | | | | | | |
| Blood sampling for: | | | | | | | | | | | | | | | | |
| Hematology, Chemistry (including FPG and eGFR) | × | | × | × | × | × | × | × | × | X | × | × | X | × | | × |
| FSH (females only); C-peptide | X | | | | | | | | | | | | | | | |
| Pregnancy test (all females) ^o | X | X | X | X | X | Х | X | X | X | X | X | X | X | X | | X |
| HbA1c | X | | X | | | | | | | Х | | | X | | | X |
| Lipids, TSH, free T4, calcitonin, amylase, lipase, TBA, PT/INR/aPTT, FPI | X | | x | | х | | × | | x | x | | х | х | x | | × |
| PF-06882961 PK (pre-dose unless noted) | | | X^{m} | | X | | X^{m} | X | | X^{m} | | | \mathbf{x}^{m} | | | X |
| Banked biospecimen: Prep B1 & B2 | | | X | | | | | | | X | | | X | | | X |
| Banked biospecimen: Prep D1 (only Day 1) ⁿ | | | X | | | | | | | | | | | | | |
| Urine Sampling for: | | | | | | | | | | | | | | | | |
| Urine drug screen | X | | | | | | | | | | | | | | | |
| Urinalysis (and microscopy, reflexive) | X | | X | | X | | X | | X | Х | | Х | Х | Х | | X |
| On-site urine pregnancy test (all females)° | | × | X | × | × | × | × | × | × | X | X | X | X | × | | X |

PFIZER CONFIDENTIAL CT02-GSOP Clinical Protocol Template Phase 1 2 3 4 (05 December 2019) Page 24

- Final Protocol Amendment 2, 16 September 2022
- a. **End of Treatment:** Defined as Week 26.
- Study part and Follow-up: In Part A (Weeks 1-16) participants will be randomized and dosed with double-blinded study intervention on Day 1 and dosing will continue through 16 weeks. In Part B (Weeks 17-26) participants in Part A will continue dosing, according to randomization from Part A.
- Early termination/discontinuation: This visit applies only to participants who are enrolled/randomized and then are prematurely withdrawn from the study, ie, permanently discontinued both from the study intervention and from the study. Note: discontinuation of study intervention does not represent withdrawal from the study. If only study intervention is discontinued, the participant will remain in the study and continue with all visits and assessments (except for dosing activities and assessment of PK). See ပ
- Days relative to Dosing on Day 1: Dosing occurs on Day 1 and timing of subsequent visits is determined by adding the number of days noted to Day 1. For example, V4 is Day 1+14 days (± 3 days), V5 is Day 1+28 days (± 3 days), etc. ġ.
- e. Follow-up V15: Visit may be a phone call. f. Site based PROs: Completed at the site on
- Site based PROs: Completed at the site on an electronic tablet. Participants at ex-US sites will only complete the SF-36v2®. Participants at US sites will complete all PRO assessments (SF-36v2®, PGI-S, PGI-C, PROMIS® Fatigue, PROMIS® Physical Function, IWQOL-Lite-CT©). See Section 8.1.3 for more details.
- Physical examination: Complete physical examination performed according to the SoA, with height measured at V1 only. A limited physical examination is performed at follow-up V14 and may be performed at non-specified visits if there are findings during the previous exam or new/open AEs, if appropriate and at investigator discretion. ьio
- **Body weight:** The second weight measurement should be obtained at least 1-2 minutes apart from the first weight measurement. Ę.
- Supine vital signs (BP and pulse rate): At V3, V7, V10 and V13, triplicate vital signs will be measured pre-dose and triplicate vital signs will be measured 1 time within the window of approximately 2-6 hours post-doze (around the same time as post-dose PK samples are collected and according to the chronology in Appendix 9).
- Eating-Related Factors Daily Diary: Only participants at selected US sites will complete this PRO diary, which will be done daily at home on a handheld device.
- Study intervention: For V2 only, study intervention reflects single blinded placebo. For V3 through V12, study intervention is dispensed via IRT and reflects double-blinded randomized PF-06882961 or placebo.
- Dispensation of study intervention at V10-V12 (Weeks 16-22): For V10-12 only, study intervention dispensation via IRT will be permitted only after formal agreement with regulatory authorities and IRBs/ECs as described in "b" above.
- PK sampling: At V3, V7, V10 and V13, PK samples will be collected pre-dose and one time within the window of approximately 2-6 hours post-dose (around the same time as post-dose vital sign measurements and according to the chronology in Appendix 9). ij.
 - Banked biospecimen Prep D1: If not collected on the designated collection day, collect at the next available time point when biospecimens are being collected in conjunction with a participant visit. 'n.
- Pregnancy tests: Serum and urine pregnancy tests are required for all females regardless of childbearing potential. For the on-site urine pregnancy tests performed at each visit V2 through V14, the test result must be negative in order to continue participation in the study. ö

1.3.2. SoA for Cohort 3

| Protocol Activity (See Appendix 11 for abbreviations) | Screening Phase | ning ase | | | | | | | Tre | Treatment Phase | ıt Pha | se | | | | | | | | | Early Term/ |
|---|---------------------|---------------|---------------------------|------------|----------|----------|----------|------------|-------------|-----------------|----------|----------|-----------------|------------------|-------------|--------------|-------------|---------------------------------------|-------------|-------------|---|
| | Screen Pbo run-i | Pbo run-in | | | | | | | | | | | | | | | | End of Treat- ment ^a | | Follow-up | Dis- cont- inua- tion ^b |
| Weeks Relative to Dosing on Day 1 | | | 0 | 2 | 4 | 9 | ∞ | 10 1 | 12 1. | 14 16 | | 18 2 | 20 2 | 22 24 | t 26 | 5 28 | 30 | 32 | 33- 34 | 36-37 | ET |
| Days Relative to Dosing on Day 1° | -42 to -15 | -14±3 | 1 | 14± 3 | 28± 4 | 42± 5 | 56±3 7 | 70± 8, | 84± 98 3 | 98±3 112± | | 126± 14 | .40± 154 3 3 | 154± 168 3 ±3 | 8 182± | 2± 196 ±3 | 6 210± | 224±3 | 231- 238 | 252- 259 | |
| Visit ("T" denotes telephone contact) ^d | V1 | V2 | V3 | V4- T | NS V | -9A T | V7 \ | V8- V T | V9 V1 T | V10- V11 T | > | | V13 V14 T | .4- V15 | 5 V16- T | 6- V17 | 7 V18- T | - V19 | V20 | V21- T | |
| Informed consent & demography | × | | L | | | H | | H | \vdash | H | \vdash | \vdash | H | H | H | H | L | L | L | | Г |
| Review of eligibility criteria | Х | X | X | | | | | | | | \vdash | | \vdash | | | | | | | | |
| Medical history | х | | | | | | | | | | | | | | | | | | | | |
| SF-36v2® (all sites) ^e | | X | X | | | | | Н | | X | | H | Н | Х | | | | х | | | |
| PGI-S (US only) ^e | | X | Х | | Х | | X | . , | х | Х | | - | х | X | | X | | Х | | | |
| PROMIS®, IWQOL-Lite-CT® (US only) | | X | X | | | | | | | X | | Н | Н | X | | | | х | | | |
| PGI-C (US only) ^e | | | | | X | | | Н | H | X | | Н | Н | х | | | | х | | | |
| Open-ended inquiry for AEs | х | ↑ | ↑ | ↑ | 1 |  | ↑ |  | 1 | ↑ | _ |   |   | ↑ | 1 |  | 1 | ↑ | \uparrow | х | х |
| Review prior/concomitant treatments | х | X | Х | X | X | X | X | X | x | X X | | X > | x x | X | X | X | X | X | Х | X | Х |
| Review drug, alcohol, tobacco use | X | X | х | | X | | x | | х | X | | 7 | x | X | | x | | X | X | х | Х |
| Review contraception use (females only) | х | X | X | X | X | X | X | X | x | X X | Н | X Y | X X | X | X | × | X | x | X | X | Х |
| Mental health questionnaires (C-SSRS, PHQ-9) | х | x | Х | | X | | х | | × | × | | | × | × | | х | | x | x | | х |
| Physical examination ^f | х | | Х | | | | | | | X | | | Н | | | | | Х | X | | Х |
| Body weight (in duplicate) ^g | х | X | X | | X | | X | | X | X | | | X | X | | X | | х | X | | Х |
| Waist and hip circumference (in triplicate) | Х | | X | | × | | × | | x | × | ., | F-1 | × | X | | X | | X | X | | х |
| Supine 12-lead ECG (pre-dose) | х | X | X | | X | | X | . , | X | X | | | X | X | | Х | | х | X | | Х |
| Supine vital signs (in triplicate) (pre-dose unless noted) | х | X | \mathbf{x}^{h} | | x | | x^{h} | | x | x | ч | F-1 | × | X | | х | | x^{h} | X | | х |
| Registration in trial (via IRT) | х | | | | | | | | | | \dashv | | | | | | | | | | |
| Eating-Related Factors Daily Diary (US only) ⁱ | | X | ↑ | \uparrow | ↑ | ↑ | ↑ |  | ↑ ↑ | ↑ | | ↑ | ↑ | ↑ | ↑ | ↑ | ↑ | X | | | |
| | | | | | | | | | | | | | | | | | | | | | |

PFIZER CONFIDENTIAL CT02-GSOP Clinical Protocol Template Phase 1 2 3 4 (05 December 2019) Page 26

| Protocol Activity (See Annendix 11 for abhreviations) | Screening Phase | reening Phase | | | | | | | Trea | Treatment Phase | Phase | | | | | | | | | | Early Term/ |
|--|--------------------|------------------|---------------------------|-----------|----------|---------------------------|---|-------------|-------------|---------------------------|-----------|------|-----------|---------------------------|-----------|-----------|-----------|---------------------------------------|-------------|-------------|----------------|
| | Screen | Pbo run-in | | | | | | | | | | | | | | | | End of Treat- ment ^a | Follo | Follow-up | |
| Weeks Relative to Dosing on Day 1 | | | 0 | 2 | 4 | 8 9 | | 10 12 | 2 14 | 16 | 18 | 20 | 22 | 24 | 26 | 28 | 30 | 32 | 33- 34 | 36-37 | LЭ |
| Days Relative to Dosing on Day 1° | -42 to -15 | -14±3 | 1 | 14± 2 | 28± 47 | 42± 56±3 3 | | 70± 84± 3 | + 98±3 | 3 112± 3 | ± 126± | 140± | 154± | = 168 ±3 | 182± 3 | 196 ±3 | 210± 3 | 224±3 | 231- 238 | 252- 259 | |
| Visit ("T" denotes telephone contact) ^d | V1 | V2 | V3 | V4- T | V5 V | V6- V7 | | V8- V9 T | 9 V10- T | - V11 | V12- T | V13 | V14- T | V15 | V16- T | V17 | V18- T | V19 | V20 | V21- T | |
| Dietary & physical activity counseling | | x | Х | П | X | X | 1.4 | Х | | X | Ш | Х | | Х | | Х | | X | | | |
| Review dosing diary | | x | X | Х | X | X X | X X | X | X : | X | X | X | X | X | X | Х | X | X | | | X |
| Randomization in trial (via IRT) | | | Х | | | | | Н | | | | | | | | | | | | | |
| Dispense study intervention supply & dosing diary | | \mathbf{x}^k | x | | x | x | , , , , , , , , , , , , , , , , , , ,  | Х | | x | | x | | х | | х | | | | | |
| Dose study intervention on site (with food) | | X | X | | х | x | u l | Х | | x | | × | | х | | х | | Х | | | |
| Compliance check of returned study intervention | | | х | | x | x | , | Х | | х | | x | | х | | х | | X | | | x |
| Blood sampling for: | | | | | | | | | | | | | | | | | | | | | |
| Hematology, Chemistry (including FPG and eGFR) | x | | × | | × | x | y . | × | | × | | × | | х | | x | | Х | X | | x |
| FSH (females only); C-peptide | Х | | | \exists | \dashv | \dashv | \dashv | \dashv | \Box | | | | | | | | | | | | |
| Pregnancy test (all females) ¹ | Х | Х | X | | X | X | L. | X | | × | | X | | Х | | Х | | X | X | | X |
| HbA1c | Х | | X | | | | | | | X | | | | X | | | | X | | | X |
| Lipids, TSH, free T4, calcitonin, amylase, lipase, TBA, PT/INR/aPTT, FPI | х | | × | | × | X | м | × | | × | | × | | х | | х | | х | x | | x |
| PF-06882961 PK (pre-dose unless noted) |) | | \mathbf{x}^{m} | | X | \mathbf{x}^{m} | m | X | | \mathbf{x}^{m} | | X | | $\mathbf{x}^{\mathbf{m}}$ | | Х | | X^{m} | | | X |
| Banked biospecimen: Prep B1 & B2 | | | X | H | Н | | | Н | | Х | Ш | | Ш | | | | | X | | | X |
| Banked biospecimen: Prep D1 (only Day 1) ^a | | | x | | | | | | | | | | | | | | | | | | |
| Urine Sampling for: | | | | | | | | | | | | | | | | | | | | | |
| Urine drug screen | Х | | ┨ | \dashv | \dashv | \dashv | \dashv | \dashv | \dashv | _ | _ | _ | | \Box | | | | | | | |
| Urinalysis (and microscopy, reflexive) | X | | × | \dashv | × | × | ,, | × | _ | × | | × | | × | | × | | X | × | | × |

PFIZER CONFIDENTIAL CT02-GSOP Clinical Protocol Template Phase 1 2 3 4 (05 December 2019) Page 27

| Protocol Activity (See Appendix 11 for abbreviations) | Scree Ph | Screening Phase | | | | | | | Tr | Treatment Phase | t Phas | 96 | | | | | | Fnd of | | | Early Term/ |
|--|----------------------|--------------------|----|-----|------|-------|------|----------|---------------------------------|---|--------|-------|-------|--------|-------|-------|------------------------|---|-----------|------|---|
| | Screen Pbo run-in | Pbo run-in | | | | | | | | | | | | | | | | Treat- Follow-up | Follor | | Dis- cont- inua- tion ^b |
| Weeks Relative to Dosing on Day 1 | | | 0 | 2 | 4 | 9 | 8 | 10 | 12 | 0 2 4 6 8 10 12 14 16 18 20 22 24 26 28 | 5 18 | 3 20 | 22 | 24 | 26 | 28 | 30 | 32 | 33- 36-37 | 6-37 | ET |
| | | | | | | | | | | | | | | | | | | | 34 | | |
| Days Relative to Dosing on Day 1 ^c | -42 to | -42 to -14±3 | 1 | 14± | 78∓ | 12± 5 | €∓9 | 8 ∓0∠ | 1 14± 28± 42± 56±3 70± 84± 98±3 | 3 112 | £ 126 | ± 140 | ± 154 | ± 168 | 3 182 | ₹ 196 | 210± | 112± 126± 140± 154± 168 182± 196 210± 224±3 | 231- 252- | 252- | |
| | -15 | | | 3 | 3 | 3 | | 3 | 3 | 3 | 3 | 3 | 3 | ±3 | 3 | ±3 | 3 | | 238 | 259 | |
| Visit ("T" denotes telephone contact) ^d | V1 | V2 | V3 | V4- | . SA | -9/ | V7 \ | 87 | V9 V | V3 V4- V5 V6- V7 V8- V9 V10- V11 V12- V13 | 1 V1 | 2- V1 | 3 V1 | 1- V1; | 5 V16 | - V17 | V14- V15 V16- V17 V18- | V19 | V20 V21- | V21- | |
| | | | | Τ | | Τ | | T | | T | T | | T | | Ι | | \mathbf{I} | | | Τ | |
| On-site urine pregnancy test (all | | X | X | | X | | х | | X | X | | Х | | Х | | X | | х | x | | X |
| females) ¹ | | | | | | | | | | | | | | | | | | | | | |

- End of Treatment: Defined as Week 32
- Early termination/discontinuation: This visit applies only to participants who are enrolled/randomized and then are prematurely withdrawn from the study, ie, permanently discontinued both from the study intervention and from the study. Note: discontinuation of study intervention does not represent withdrawal from the study. If only study intervention is discontinued, the participant will remain in the study and continue with all visits and assessments (except for dosing activities and assessment of PK). See
- Days relative to Dosing on Day 1: Dosing occurs on Day 1 and timing of subsequent visits is determined by adding the number of days noted to Day 1. For example, V4-T is a telephone contact at Day 1+14 days (±3 days), V5 is an in-clinic visit at Day 1+28 days (±3 days), etc ပ
- Visit: Visits with a "T" are planned as telephone contacts, while other visits are planned as in-clinic study visits. .
- Site based PROs: Completed at the site on an electronic tablet. Participants at ex-US sites will only complete the SF-36v2. assessments (SF-36v2®, PGI-S, PGI-C, PROMIS® Fatigue, PROMIS® Physical Function, IWQOL-Lite-CT®). See Section 8.1.3 for more details. ij
- Physical examination: Complete physical examination performed according to the SoA, with height measured at V1 only. A limited physical examination is performed at follow-up V20 and may be performed at non-specified visits if there are findings during the previous exam or new/open AEs, if appropriate and at investigator discretion. Ŧ
- **Body weight:** The second weight measurement should be obtained at least 1-2 minutes apart from the first weight measurement. ьio
- Supine vital signs (BP and pulse rate): At V3, V7, V11, V15 and V19, triplicate vital signs will be measured pre-dose and triplicate vital signs will be measured 1 time within the window of approximately 2-6 hours post-dose (around the same time as post-dose PK samples are collected and according to the chronology in Appendix 9). Ъ.
- Eating-Related Factors Daily Diary: Only participants at selected US sites will complete this PRO diary, which will be done daily at home on a handheld device.
- Dosing diary review: For telephone visits, this review consists of site staff reminding participants to record doses taken as well as any missed doses in their dosing diary and to bring the diary to in-clinic study visits. For onsite visits, site staff should review the returned dosing diary entries with participants.
- Study intervention: For V2 only, study intervention reflects single blinded placebo. For V3, V5, V7, V9, V11, V13, V15 and V17, study intervention is dispensed via IRT and reflects double-blinded randomized PF-06882961 or placebo. 7
- Pregnancy tests: Serum and urine pregnancy tests are required for all females regardless of childbearing potential. For the on-site urine pregnancy tests performed at each planned in-clinic visit V2 through V20, the test result must be negative in order to continue participation in the study.

- **PK sampling:** At V3, V7, V11, V15 and V19, PK samples will be collected pre-dose *and* 1 time within the window of approximately 2-6 hours *post-dose* (around the same time as post-dose vital sign measurements and according to the chronology in Appendix 9). Ħ.
 - Banked biospecimen Prep D1: If not collected on the designated collection day, collect at the next available time point when biospecimens are being collected in conjunction with a participant visit. 'n.

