5.1. Inclusion Criteria

Participants are eligible to be included in the study only if all of the following criteria apply:

Age and Sex:

- 1. Male or female participants between the ages of 18 (or the minimum country-specific age of consent if >18) and 75 years, inclusive, at V1.
 - Women can be of child-bearing potential, however, cannot be pregnant, breastfeeding, or planning to become pregnant while participating in the study.
 - Refer to Appendix 4 for reproductive criteria for male (Section 10.4.1) and female (Section 10.4.2) participants.

Type of Participant and Disease Characteristics:

2. Willing and able to comply with all scheduled visits, treatment plan, laboratory tests, lifestyle considerations, and other study procedures.

Body Mass Index (BMI) and Weight:

- 3. Participants with obesity, defined as a BMI \geq 30.0 kg/m² at V1.
- 4. Stable body weight, defined as <5 kg change (per participant report) for 90 days before V1.

Informed Consent:

5. Capable of giving signed informed consent as described in Appendix 1, which includes compliance with the requirements and restrictions listed in the ICD and in this protocol.

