7. DISCONTINUATION OF STUDY INTERVENTION AND PARTICIPANT DISCONTINUATION/WITHDRAWAL

7.1. Discontinuation of Study Intervention

It may be necessary for a participant to permanently discontinue study intervention. Reasons for permanent discontinuation of study intervention include the following:

- Criteria for a potential Hy's law case are met (see Appendix 6);
- Intent to become pregnant or pregnancy confirmed by β-hCG testing;
- Safety or tolerability concern arises, in particular if not responsive to symptomatic management, dosing with double-blind study intervention may be stopped in an individual participant at the discretion of the investigator;
- Based on mental health assessment as outlined in Section 8.2.6, should be discontinued from dosing at the discretion of the investigator.

If the criteria for permanent discontinuation are met, the site should notify the sponsor Medical Monitor or sponsor Clinician.

Note that discontinuation of study intervention does not represent withdrawal from the study. If study intervention is definitively discontinued, the participant will remain in the study to be evaluated for obesity, and will be expected to continue with all study visits and assessments as outlined in the SoA for the applicable cohort (see SoA for Cohorts 1 and 2, and SoA for Cohort 3), with the exception of dosing activities and assessment of PK. See the SoA for the applicable cohort (see SoA for Cohorts 1 and 2, and SoA for Cohort 3) for data to be collected at the time of discontinuation of study intervention and follow-up for any further evaluations that need to be completed.

In the event of discontinuation of study intervention, it must be documented on the appropriate CRF/in the medical records whether the participant is discontinuing further receipt of study intervention or also from study procedures, posttreatment study follow-up, and/or future collection of additional information.

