7.2. Participant Discontinuation/Withdrawal From the Study

A participant may withdraw from the study at any time at his/her own request. Reasons for discontinuation from the study include the following:

- Refused further follow-up;
- Lost to follow-up;
- Death:
- Study terminated by sponsor;
- Safety or behavioral reasons at the discretion of the investigator, including reasons related to mental health assessments as described in Section 8.2.6.

At the time of discontinuing from the study, if possible, an early discontinuation visit should be conducted. See the SoA for the applicable cohort (see SoA for Cohorts 1 and 2, and SoA for Cohort 3) for assessments to be collected at the time of study discontinuation and follow-up and for any further evaluations that need to be completed.

The early discontinuation visit applies only to participants who are enrolled/randomized and then are prematurely withdrawn from the study. Participants should be questioned regarding their reason for withdrawal. The participant will be permanently discontinued both from the study intervention and from the study at that time.

If a participant withdraws from the study, he/she may request destruction of any remaining samples taken and not tested, and the investigator must document any such requests in the site study records and notify the sponsor accordingly.

If the participant withdraws from the study and also withdraws consent (see Section 7.2.1) for disclosure of future information, no further evaluations should be performed and no additional data should be collected. The sponsor may retain and continue to use any data collected before such withdrawal of consent.

Lack of completion of all or any of the withdrawal/early termination procedures will not be viewed as protocol deviations so long as the participant's safety was preserved.

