7.2.1. Withdrawal of Consent

Participants who request to discontinue receipt of study intervention will remain in the study and must continue to be followed for protocol-specified follow-up procedures. The only exception to this is when a participant specifically withdraws consent for any further contact with him or her or persons previously authorized by the participant to provide this information. Participants should notify the investigator in writing of the decision to withdraw consent from future follow-up, whenever possible. The withdrawal of consent should be explained in detail in the medical records by the investigator, as to whether the

withdrawal is only from further receipt of study intervention or also from study procedures and/or posttreatment study follow-up, and entered on the appropriate CRF page. In the event that vital status (whether the participant is alive or dead) is being measured, publicly available information should be used to determine vital status only as appropriately directed in accordance with local law.

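### After randomization, the SoA pregnancy footnotes make a negative urine test a condition of staying in the study, while Section 7.1 stops study drug for pregnancy and keeps the participant in the study

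*Protocol*

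**What the plan says.** **SoA pregnancy footnotes (Protocol 1.3.1 and 1.3.2).** Serum and urine tests are required in all females, whatever their childbearing potential. For the on-site urine test, "the test result must be negative in order to continue participation in the study". The rule runs from V2 through V14 in Cohorts 1 and 2, and over the in-clinic visits V2 through V20 in Cohort 3. It names no confirmatory test.

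**Section 7.1.** The reasons for permanently stopping study intervention include "Intent to become pregnant or pregnancy confirmed by β-hCG testing". The consequence is then stated: "If study intervention is definitively discontinued, the participant will remain in the study to be evaluated for obesity". All visits and assessments continue except dosing and PK.

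**SoA early-termination footnotes (1.3.1 and 1.3.2).** These give the general rule that "discontinuation of study intervention does not represent withdrawal from the study", and add: "If only study intervention is discontinued, the participant will remain in the study and continue with all visits and assessments". They do not mention pregnancy.

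**Section 7.2.** The list of reasons for leaving the study opens with "Reasons for discontinuation from the study include the following". Pregnancy is not on it. It does contain safety reasons at the investigator's discretion.

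**Section 8.2.7.** Urine and serum tests are both used, with a common minimum sensitivity. The section gives no rule for a positive result after randomization.

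**Inclusion criterion 1 (Section 5.1).** Women "cannot be pregnant, breastfeeding, or planning to become pregnant while participating in the study".

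**The concern.** A randomized woman with a positive on-site test has two different study statuses depending on which page the site opens. The footnote takes her out of the study. Section 7.1 takes her off drug and keeps her in. Section 8 calls adherence to the SoA essential and allows no waivers, so a site that follows 7.1 departs from its SoA, and a site that follows the SoA departs from 7.1.

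Three things are at stake. A drug-exposed pregnant woman could lose her scheduled off-drug safety visits at one site and keep them at another. A woman with a false-positive urine result, including one who cannot be pregnant, could be removed; Section 9.2 says withdrawn participants are not replaced. And the same event could be coded as study withdrawal at one site and as drug discontinuation at another. The SAP reports these separately, with time to study discontinuation and time to IP discontinuation each plotted (Section 6.6.2, Discontinuations).

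**Working it through.** The plan states no figure to reproduce. The check compares rules and counts the visits affected.

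**Step 1: the two rules side by side.**

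| | SoA pregnancy footnotes | Section 7.1 |
|---|---|---|
| Trigger | On-site urine result that is not negative | Intended pregnancy, or pregnancy confirmed by β-hCG testing |
| Consequence | Participation in the study does not continue | Study intervention stops; participant stays, without dosing or PK |
| When | V2 through V14 or V20 | No visit range given |

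The consequences cannot both hold. The triggers differ less sharply. Table 6 (Appendix 2) attaches the β hCG label to the serum test only, which suggests serum confirmation, but 7.1 does not say serum.

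**Step 2: does another section decide between them?**
- Section 7.2 permits withdrawal by discretion. It does not make withdrawal the default for pregnancy.
- Section 7.2.1 sets the stay-in default for those who ask to stop drug: "Participants who request to discontinue receipt of study intervention will remain in the study and must continue to be followed for protocol-specified follow-up procedures". It does not address pregnancy.
- Section 8.2.7 covers which tests are done, not what follows a positive one.
- Criterion 1 is an entry criterion. Eligibility review is scheduled only at V1 to V3, and no consequence after randomization is attached to it.

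None resolves it. At V2 and pre-dose V3 there is no conflict, because the footnote acts there as an eligibility check.

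**Step 3: post-randomization visits affected.**
- Cohorts 1 and 2: urine tests at V4 to V14 = 11. V14 follows the end of dosing, so 11 − 1 = 10 visits (V4 to V13) where the rules compete over stopping drug.
- Cohort 3: V5, V7, V9, V11, V13, V15, V17, V19 and V20 = 9. V20 follows the end of dosing, so 9 − 1 = 8.
- At V14 and V20, 7.1 has no drug left to stop. Only the last contact (V15 or V21-T) depends on the footnote.

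**Step 4: scheduled follow-up that 7.1 keeps and the footnote ends, per case (nominal days).**
- Cohort 3, positive at V5 (Day 28): 8 in-clinic visits (V7, V9, V11, V13, V15, V17, V19, V20) and 8 telephone contacts (V6, V8, V10, V12, V14, V16, V18, V21). Span to V21: 252 − 28 = 224 to 259 − 28 = 231 days.
- Cohort 3, positive at V17 (Day 196): 2 in-clinic (V19, V20) and 2 telephone (V18, V21). Span: 252 − 196 = 56 to 259 − 196 = 63 days.
- Cohorts 1 and 2, positive at V4 (Week 2): V5 to V14 = 10 in-clinic visits plus V15. Span: 30 − 2 = 28 to 31 − 2 = 29 weeks.

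These are schedule lengths, not measures of harm. Under the footnote she would still have an early-termination visit where possible.

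**Step 5: a side effect of retention.** Section 7.1 excludes only dosing and PK, so counseling toward a deficit of at least 500 kcal/day (Section 5.3.2) stays on the schedule. After V5 in Cohort 3 it falls at V7, V9, V11, V13, V15, V17 and V19 = 7 visits. After V4 in Cohorts 1 and 2 it falls at V5, V7, V9, V10, V11, V12 and V13 = 7 visits. Clarified wording has to switch this off.

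**Step 6: the primary analysis.** Estimand Set 1 censors values after study intervention stops (Protocol 9.3, SAP Section 4). A confirmed pregnancy therefore contributes no later weights under either rule. Only a false-positive removal would lose weights that the analysis would otherwise use.

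**The case against.** The strongest reply is that the protections that matter do not depend on the footnote. Highly effective contraception is required for women of childbearing potential (10.4.2). Adverse events are collected for at least 28 days after the last dose (8.3.1). Exposure during pregnancy is reported within 24 hours and followed to outcome (8.3.5.1). The early-termination visit includes examination, ECG, vital signs, laboratory tests and mental health questionnaires. Section 7.1 requires the site to record whether drug alone or also study procedures have stopped. All of this stands, and it is why the point is minor.

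It can also be said that serum is drawn at the same visit and nothing forbids waiting for it, so removal on an unconfirmed urine result follows only from the most literal reading. That is fair, and it softens the trigger conflict. It leaves open whether a confirmed case stays or leaves.

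Finally, criterion 1 refers to the time of participation and the 7.2 list is open, so ending participation could be what the sponsor intends. That would be a coherent policy, but 7.1 says the opposite for the same event. Permission to withdraw at discretion does not reconcile a mandatory exit with a stated default of staying.

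A reader might go further and infer that exposed pregnancies go unfollowed, that the weight-loss estimate is biased, that the early-termination footnotes themselves address pregnancy, or that 7.1 acts only on confirmed pregnancy by serum test. The documents support none of these. Sections 8.3.1 and 8.3.5.1 apply either way, later weights are censored, those footnotes are silent on pregnancy, and 7.1 also covers intent and does not specify serum.

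**Conclusion.** The contradiction is real and sits in the current text of both SoAs and Section 7.1. It is firm on leaving versus staying and softer on the trigger. It bears on stopping drug at 10 visits in Cohorts 1 and 2 and 8 in Cohort 3, and on one remaining contact after V14 or V20.

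The consequence is minor. The documents give no event count. That events will be few is an assumption resting on the contraception requirement, and a negligible effect on the primary estimate rests on that assumption together with the censoring rule. What is left is inconsistent site conduct, disposition coding, scheduled off-drug safety visits, and possible removal of a participant on a false-positive urine result. Cohorts 1 and 2 are described as already randomized, so the practical gain is mainly in Cohort 3.

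**What to change.** In both SoA pregnancy footnotes, limit the condition that "the test result must be negative in order to continue participation in the study" to V2 and pre-dose V3. For later visits, substitute wording such as:

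> If the on-site urine test is positive, withhold study intervention (where still being dosed) until the result of the serum β-hCG test scheduled at that visit is available. If pregnancy is confirmed, discontinue study intervention and follow the participant per Section 7.1, with reporting per Section 8.3.5.1; energy-deficit dietary counseling is not given. If pregnancy is not confirmed, the participant continues.

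Criterion 1 can stand as an entry criterion.

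The cost is new wording in two footnotes. No test is added, because serum testing is already scheduled at the same in-clinic visits. There may be a short dosing gap while the serum result is awaited; the documents give no turnaround time. If the on-site dose is withheld, that visit's post-dose PK sample and vital signs may be missed. After randomization this concerns V7, V10 and V13 in Cohorts 1 and 2, and V7, V11, V15 and V19 in Cohort 3.
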